### **5.7. Subject Withdrawal/Discontinuation**

#### **5.7.1. Reasons for Withdrawal**

Any subject who discontinues from the study drug for any reason will have their study drug discontinuation recorded.

The date of discontinuation of treatment (EOT) is defined as the date the Investigator decides to discontinue treatment.

Subjects may be withdrawn from the study after signing informed consent for the following reasons:

- PD (per RECIST)
- Clinical Progression (provide date)
- AE
- Death
- Withdrawal by subject
- Lost to F/U
- Protocol violation (specify)
- Physician Decision
- Pregnancy
- Study terminated by the Sponsor
- Other, specify (eg, discretion of the Investigator)

If a subject withdraws from the study, the Investigator will complete and report the observations as thoroughly as possible up to the date of withdrawal including the date of last treatment and the reason for withdrawal.

If the subject is withdrawn due to an AE, the Investigator will follow the subject until the AE has resolved or stabilized as possible.

All subjects who are withdrawn from the study and received study drug should complete the protocol specified withdrawal procedures (Section [5.7.2](#)).

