### **6.3.1. Tumor Assessment**

The same imaging tumor assessment as at Screening by CT or MRI scans will be performed every 6 weeks ( $\pm 7$  days) in the first 24 weeks after Day 1 of Cycle 1 and thereafter every 12 weeks ( $\pm 7$  days) regardless of a delay in dosing. The assessment will be conducted before Day 1 of each Cycle if possible. CT or MRI (spiral CT or MRI with  $\leq 5$  mm cuts) of the brain, chest, abdomen, and pelvis and other areas of disease should be used for tumor assessments unless another modality of disease assessment is necessary for the lesions at Screening. Every effort should be made to use the same assessment modality for all assessments for each subject, and confirmatory scan are required for responding patients. However, if there is no brain metastasis at Screening, CT or MRI should only be done when symptoms associated with brain metastasis occur during study period. If no clinical symptoms are observed, brain CT or MRI is not mandatory during study period (Section 17.4).

Detailed instructions for the handling of images are included in a separate document.

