- Perform same imaging tumor assessment as at Screening by CT or MRI scans. CT or MRI (spiral CT or MRI with  $\leq 5$  mm cuts) of the brain, chest, abdomen, and pelvis should be used for tumor assessments unless another modality of disease assessment is necessary for the lesions at Screening. Every effort should be made to use the same assessment modality for all assessments for each subject. However, if there is no brain metastasis at Screening, CT or MRI should only be done when symptoms associated with brain metastasis occur during study period. If no clinical symptoms are observed, brain CT or MRI is not mandatory during study period (Section 17.4). If progression is identified in a prior examination, only the chest is examined by CT to monitor the pulmonary status.
- Record concomitant medications.
- Assess subjects for AEs.
- Record reason for treatment discontinuation.

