## 6.5. Follow-up

The F/U visit should occur 40 days (+ 7 days) days after the last administration of DS-8201a. If the subject begins another anticancer therapy before the end of the 40 days (+ 7 days), every effort will be made to complete all the F/U assessments prior to commencing the new therapy. In case of unresolved AEs, including significant abnormal clinical laboratory values at the end of study assessment, these events will be followed until resolution or until they become clinically not relevant. If assessments at EOT or treatment period are performed within this period, they can be considered to be the F/U data and there is no need to repeat them. If discontinuation of treatment is decided later than 40 days after the last administration of DS-8201a, there is no need to perform the F/U assessments.

The following information will be collected at this F/U visit:

- Obtain vital sign measurements (systolic and diastolic blood pressure and pulse rate, respiratory rate and body temperature).
- Perform a complete physical examination and record the subject's weight.
- Assess functional status using the ECOG PS scale (Section 17.3).
- Obtain blood samples for clinical laboratories (Section 8.8) and ADA (Section 7.4.1). For subjects with positive ADA at F/U visit, additional serum ADA samples may be collected every 3 months ( $\pm 1$  month) up to 1 year from the last dose of study drug, or if the ADA becomes negative, or if ADA titer becomes less than Baseline (applicable when pre-existing ADA is observed), or if the subject starts another therapy for cancer, or withdraws consent from the study, whichever occurs first. A portion of ADA blood sample from each subject who provides consent will be used for future central lab analysis for SARS-CoV-2 testing once protocol version 5.0 is applied for a subject. SARS-CoV-2 testing will be conducted every 4 cycles from Cycle 4 (Cycle 4, Cycle 8 etc.).
- Obtain a serum or urine sample for pregnancy testing in women of childbearing potential. For postmenopausal subjects (no childbearing potential, as indicated by an elapse of at least 12 months after the last

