### **8.2. Adverse Event Collection and Reporting**

All clinical AEs occurring after the subject signs the ICF and up to the F/U visit after the last dose of study drug (ie, the F/U period) defined as 40 + 7 days, whether observed by the Investigator or reported by the subject, will be recorded on the AE Case Report Form (CRF) page. Medical conditions (including clinical laboratory values/vital signs that are out of range) that were diagnosed or known to exist prior to informed consent will be recorded as part of medical history.

All AEs and SAEs are to be reported according to the procedures in Section 8.5.

All clinical laboratory results, vital sign measurements, and ECG results should be assessed by the Investigator to determine their clinical significance. Isolated abnormal clinical laboratory results, vital signs, or ECG findings (ie, not part of a reported diagnosis) should be reported as AEs if they are symptomatic, lead to study drug discontinuation, dose reduction, require corrective treatment, or constitute an AE in the Investigator's clinical judgment.

At each time point, the Investigator will determine whether any AEs have occurred by evaluating the subject. AEs may be directly observed, reported spontaneously by the subject or by questioning the subject at each time point. Subjects should be questioned in a general way, without asking about the occurrence of any specific symptoms. The Investigator must assess all AEs to determine seriousness, severity, and causality, in accordance with the definitions in Section 8.4. The Investigator's assessment must be clearly documented in the study site's source documentation with the Investigator's signature.

Always report the diagnosis as the AE or SAE term. When a diagnosis is unavailable, report the primary sign or symptom as the AE or SAE term with additional details included in the narrative until the diagnosis becomes available. If the signs and symptoms are distinct and do not suggest a common diagnosis, report them as individual entries of AE or SAE.

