#### DoR, PFS and OS:

DoR is defined as the time from the date of the first documentation of objective response (CR or PR) to the date of the first objective documentation of PD. DoR will be measured for responding subjects (CR or PR) only. Detailed censoring rules for DoR will be specified in the SAP.

PFS is defined as the time interval from the date of the first dose of the study drug to the date of first objective documentation of radiographic PD or death due to any cause. Detailed censoring rules for the PFS analysis will be specified in the SAP.

OS is defined as the time interval from the date of the first dose to the date of death for any cause. Subjects will be censored at the time last known to be alive if the subjects have not been reported to have died by the time of cutoff for the primary analysis.

The time-to-event variables, including DoR, PFS and OS will be summarized descriptively using the Kaplan-Meier method to provide the median event time and the corresponding 95% CI.

Best percent change in the sum of diameter(s) of target lesion(s):

Descriptive statistics for the best percent change in the sum of diameter(s) of target lesion(s) will be provided. A waterfall plot of the best percentage change from Screening in the sum of the longest dimensions (SLD) for each subject will be presented.

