#### **17.4.2.7.4. Special Notes on Response Assessment**

When nodal disease is included in the sum of target lesions and the nodes decrease to 'normal' size (<10 mm), they may still have a measurement reported on scans. This measurement should be recorded even though the nodes are normal in order not to overstate progression should it be based on increase in size of the nodes. As noted earlier, this means that subjects with CR may not have a total sum of 'zero' on the CRF.

Subjects with a global deterioration of health status requiring discontinuation of treatment without objective evidence of disease progression at that time should be reported as "symptomatic deterioration". Every effort should be made to document objective progression even after discontinuation of treatment. Symptomatic deterioration is not a descriptor of an objective response: it is a reason for stopping study therapy. The objective response status of such subjects is to be determined by evaluation of target and non-target disease. If a radiographic tumor assessment has not been performed within 4 weeks of the time of clinical progression, then another radiographic assessment should be performed without waiting for the next regularly scheduled scan.

For equivocal findings of progression (eg, very small and uncertain new lesions; cystic changes or necrosis in existing lesions), treatment may continue until the next scheduled assessment. If at the next scheduled assessment, progression is confirmed, the date of progression should be the earlier date when progression was suspected.

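### Duration of response ends only at documented progression, while PFS ends at progression or death, so a responder who dies without documented progression is an event for PFS but not for DoR

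*Combined protocol and SAP*

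**What the plan says.** Section 11.4.1 (DoR, PFS and OS) measures DoR in responders only, from first documented CR or PR "to the date of the first objective documentation of PD". The following paragraph ends PFS at "first objective documentation of radiographic PD or death due to any cause". Both endpoints, with OS, are summarised by Kaplan-Meier median and 95% CI. Detailed censoring rules for DoR and PFS are left to the SAP, and no such rules appear in the text available.

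DoR is also named in the synopsis and in Sections 2.3.4, 3.2.3, 9.1 and 11.4.1 (opening paragraph). None of these gives an end event, so the definition above is the only one. Section 2.3.4 lists DoR as exploratory.

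**The concern.** The two definitions stand next to each other and classify the same subject differently. For DoR, a responder's death without documented progression must be censored or dropped. Censoring it treats the response as if it would have continued as it did in the survivors, which usually makes responses look longer than they were.

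The situation can occur:

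- Section 5.7.1 lists death as a withdrawal reason separate from RECIST progression. It also lists "Clinical Progression (provide date" separately, so a subject can stop treatment without radiographic progression and die later.
- Scans are 6-weekly "in the first 24 weeks after Day 1 of Cycle 1 and thereafter every 12 weeks" (Section 6.3.1), so a death can fall well inside a scan interval.
- In Section 6.5, "The F/U visit should occur 40 days" after the last dose, and no tumour scan is listed for that visit. Adverse events are collected "up to the F/U visit after the last dose of study drug" (Section 8.2), so deaths are captured in a window with no planned imaging.

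Two provisions make it less likely. Section 6.4 requires imaging at end of treatment: "Perform same imaging tumor assessment as at Screening by CT or MRI scans". Section 17.4.2.7.4 says "Every effort should be made to document objective progression even after discontinuation of treatment", and asks for an extra scan at clinical progression if none is recent. Neither helps once the subject has died.

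**Working it through.** The plan attaches no figure to DoR, so there is none to reproduce. The check compares the definitions and then sizes the effect.

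**1. Classification of a responder**

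| Course after response | PFS | DoR |
|---|---|---|
| Documented radiographic PD | event | event |
| Death with no documented PD | event | not an event |
| Neither | censored | censored |

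Only the second row differs. A censoring rule says when a subject without an event leaves the risk set. It cannot by itself make death an event that the definition omits.

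**2. Expected responders.** Section 1.2.3 reports an ORR of 48.4% (HER2-positive gastric) and 61.5% (HER2-positive breast, Part 2a). With 12 subjects: 12 × 0.484 = 5.8 and 12 × 0.615 = 7.4, so about 6 or 7.

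**3. Large-sample effect.** Let *s* be the share of response endings that are deaths without PD. The documents do not give it, so 10%, 20% and 30% are assumptions. With constant, independent hazards and censoring at the death date, the PD-only median divided by the PD-or-death median is 1/(1 − *s*):

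- *s* = 0.10: 1/0.90 = 1.11
- *s* = 0.20: 1/0.80 = 1.25
- *s* = 0.30: 1/0.70 = 1.43

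**4. Small-sample simulation.** There were 12,000 trials per cell with 6 or 7 responders. Scans fall at weeks 6, 12, 18, 24, 36, 48 and so on (Section 6.3.1). First response is either all at week 6, or 60/25/15% at weeks 6/12/18 (assumed). Time from response to its end is exponential. Each ending is a death without PD with probability *s*; otherwise PD is dated at the next scan. The median is the first time S(t) ≤ 0.5. The primary cutoff is modelled as uniform accrual over 35 weeks (about 8 months, Section 3.2.1) plus 12 weeks (4 cycles, Section 11.1), with assumed median DoR of 20, 30 or 45 weeks. The no-cutoff case uses 30 weeks and is an upper case.

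Share of trials, as a range over cells:

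| PD-only median against PD-or-death median | *s* = 10% | 20% | 30% |
|---|---|---|---|
| Cutoff, death-date censoring: higher or non-estimable | 5.1–13.4% | 10.2–26.6% | 15.7–37.7% |
| Cutoff, last-scan censoring: higher or non-estimable | 5.1–13.4% | 10.1–26.6% | 15.6–37.7% |
| Cutoff, subject excluded: higher or non-estimable | 4.5–11.9% | 8.9–22.4% | 14.2–31.6% |
| Cutoff, subject excluded: lower | 0.4–3.5% | 0.8–5.2% | 1.0–5.9% |
| No cutoff, death-date censoring: higher | 21.5–25.4% | 39.9–46.3% | 55.5–62.4% |
| No cutoff, subject excluded: lower | 2.9–19.2% | 8.7–28.0% | 14.8–32.7% |

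At the cutoff the median is lower in 0% of trials with death-date censoring and in at most 0.21% with last-scan censoring. It is non-estimable under both definitions in 27.6–71.1%.

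**5. Example where the median rises.** Seven responders, all responding at week 6, have DoR of 6, 10 (death), 12, 18 and 30 weeks, with two ongoing beyond 30.

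- Death as event: S(6) = 6/7, S(10) = 5/7, S(12) = 4/7, S(18) = 3/7. Median 18.
- Censored at the death date: S(12) = 6/7 × 4/5 = 0.686, S(18) = 0.686 × 3/4 = 0.514, S(30) = 0.514 × 2/3 = 0.343. Median 30. Censoring at the last scan (DoR 6) also gives 30.

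**6. Example where handling decides the direction.** Three responders have DoR 18. One responds at week 24, has a last scan at week 36 (DoR 12) and dies at week 47 (DoR 23). Three have DoR 24, 36 and 36.

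- Death as event: S(18) = 4/7, S(23) = 3/7. Median 23.
- Censored at the death date: S(24) = 4/7 × 2/3 = 0.381. Median 24.
- Censored at the last scan, or excluded: S(18) = 3/6. Median 18 (21 by the midpoint convention).

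**The case against.** The best counter-argument is that DoR and PFS are separate endpoints and nothing obliges them to share an end event. A PD-only DoR measures time to documented progression, and OS covers death. The SAP is unseen, is to be finalised before database lock (Section 11.9) and may document changes to the planned analysis (Section 15.4), so it could already settle the matter. The death shares, hazards and response timing are all assumed. Even so, at the primary cutoff with death-date censoring, the result is unchanged or non-estimable either way in about 87–95% of simulated trials at a 10% share and 62–84% at 30%. Section 11.4.1 lists all efficacy endpoints and Section 11.4.3.1 lists deaths, so with 6 or 7 responders each case would be visible.

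Much of this stands, and it limits the consequence. It is also true that clinical progression alone, without death, is an event under neither definition and creates no discrepancy. What does not stand is that the text is adequate as written. The protocol gives no rationale for a PD-only DoR, and what it defers to the SAP is censoring rules, not the choice of event. Read literally, it excludes death and leaves at least three ways of handling it, which can give different medians.

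**Conclusion.** The point holds. As defined, a responder's death without documented progression counts for PFS and not for DoR, and median DoR will usually be unchanged or longer than under a PD-or-death definition. That direction is guaranteed only with censoring at the death date. With last-scan censoring the median is occasionally shorter, and with exclusion it can move either way.

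The size depends on assumed shares of such deaths, and the 11–43% large-sample lengthening is a guide to direction more than a forecast for about 12 subjects. No hypothesis test or sample size rests on DoR. This should be corrected, but it does not threaten the trial's main conclusion. Confidence is high on the wording and lower on the numerical effect.

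**What to change.** In Section 11.4.1, or in the SAP, let DoR run from first documented CR or PR to the earlier of first objectively documented PD and death from any cause. Make the DoR censoring rules in the SAP the same as those for PFS before database lock. If a PD-only DoR is intended, say so, justify it and state how a death without PD is handled.

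The cost is one phrase, and the deaths are already needed for PFS and OS. Median DoR will usually be unchanged or shorter than under the present wording. One limit remains: Section 6.6 makes survival follow-up not applicable, so deaths after the 40 (+7) day visit are not systematically collected. PFS and OS already share that limit, and this change does not remove it.

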#### 11.4.2. Pharmacokinetic Analyses

The PK analyses will be performed on the PK Analysis Set using actual sample times and noncompartmental methods. Serum concentration-time data for DS-8201a will be listed, and summarized using descriptive statistics by study cycle at each nominal collection time. Applicable plots will illustrate the appropriate data.

PK parameters will be estimated for both cycles. The PK parameters of DS-8201a, total anti-HER2 antibody, and MAAA-1181a (AUClast, AUC0-21d, Cmax, Tmax, and Ctrough) will be listed and summarized using descriptive statistics. AUCinf, Kel, T1/2, CL, Vz, and Vss will be estimated if determined to be appropriate. Descriptive statistics will be provided for all serum concentration data at each time point and PK parameters for each analyte as appropriate. Primary PK parameters are presented in [Table 11.1](#) and all other parameters are considered secondary.

**Table 11.1: Pharmacokinetics Parameters**

Cycle 1	
 
1. AUClast
 
2. AUC0-21d
 
3. Cmax
 
4. Tmax
 

Cycle 3	
 
1. AUClast
 
2. AUCtau
 
3. Cmax
 
4. Tmax
 

#### 11.4.3. Safety Analyses

Safety analyses will be performed on the safety analysis set. Safety endpoints will include AEs, SAEs, TEAEs, AEs and AESIs leading to discontinuation, physical examination findings (including ECOG PS), vital sign measurements, standard clinical laboratory parameters, ECG parameters, ECHO or MUGA findings and ophthalmologic assessments. AEs will be graded according to the NCI-CTCAE

version 4.03. Safety analysis in general will be descriptive and will be presented in tabular format with appropriate summary statistics.

#### **11.4.3.1. Adverse Event Analyses**

A TEAE is defined as an AE that emerges during the treatment period (from first dose date until F/U visit after the last dose of study medication), having been absent at pre-treatment; or reemerges during treatment, having been present at Baseline but stopped prior to treatment; or worsens in severity after starting treatment relative to the pre-treatment state, when the AE is continuous.

The number and percentages of subjects reporting TEAEs will be tabulated by the worst NCI-CTCAE grade, System Organ Class (SOC) and Preferred Term (PT).

Similarly, the number and percentage of subjects reporting treatment-emergent SAEs will be tabulated, as well as TEAEs/SAEs considered related to DS-8201a.

The time interval from the date of first dose of the study drug to the first onset date of AESIs will be summarized by AESI category.

A by-subject AE (including TEAE) data listing will be provided including, but not limited to, verbatim term, PT, SOC, NCI-CTCAE grade, and relationship to study drug.

Deaths, other SAEs, and other significant AEs, including those leading to permanent discontinuation from DS-8201a, will be listed.

#### **11.4.3.2. Clinical Laboratory Evaluation Analyses**

Descriptive statistics will be provided for selected clinical laboratory test results (hematology, coagulation, chemistry, and urinalysis and changes from Baseline by scheduled time of evaluation, including the EOT visit. In addition, the change from Baseline will be summarized for the maximum post-treatment value and minimum value.

Abnormal laboratory results for selected clinical laboratory tests will be graded according to the NCI-CTCAE version 4.03, if applicable. A shift table, presenting the 2-way frequency tabulation for Baseline and the worst value according to NCI-CTCAE grade, will be provided for selected clinical laboratory tests. Abnormal clinical laboratory test results that are deemed of clinical significance or of Grade 3 or 4 will be listed.

#### **11.4.3.3. Vital Sign Analyses**

Descriptive statistics will be provided for the vital sign measurements and changes from Baseline by scheduled time of evaluation, including the EOT visit. In addition, the change from Baseline will be summarized for the maximum and minimum value.

#### **11.4.3.4. Electrocardiogram Analyses**

A shift table, presenting the 2-way frequency tabulation for Baseline and each scheduled time, including the EOT visit according to the categories for ECG (normal and abnormal) will be provided. Other ECG data will be listed.

#### **11.4.3.5. Other Safety Analyses**

Abnormal ECHO or MUGA findings and ophthalmologic findings will be summarized.

ADA assessment data will be listed and summarized appropriately.

#### **11.5. Interim Analyses**

No interim analyses are planned for this study.

#### **11.6. Data Monitoring Committee**

Not applicable.

#### **11.7. Safety Monitoring Team**

There is a safety monitoring team established for the purpose of assessing safety and tolerability of subject. The meeting will be held regularly. The members may include medical expert/medical monitor of Daiichi Sankyo and medical advisor of Quintiles. This meeting will be held after 6 patients have completed Cycle 1 and when necessary. Detailed procedures will be specified in the medical monitoring plan and relative study plans.

